### **Intention-to-Treat (ITT) Set**

The intention-to-treat set comprises all subjects who received at least one dose of the vaccine or placebo. Subjects in the ITT population will be analysed according to their randomization.

## **5.4 Efficacy Endpoints Analysis Methods**

### **5.4.1 Hypothesis**

The hypothesis to be tested is:  $H_0 : VE \leq 40\%$

where VE denotes the vaccine efficacy of M-001 against qRT-PCR- or culture-confirmed influenza in association with protocol-defined ILI over a first season of influenza.

The hypothesis will be rejected and the superiority of M-001 demonstrated if the lower bound of the two-sided 95% CI for VE is  $>40\%$  for the primary per-protocol analysis.

### **5.4.2 Statistical Methods**

#### **Primary efficacy endpoint:**

The main analysis will be performed using data from cohort 1 (Season 2018-2019) and cohort 2 (Season 2019-2020) combined.

Efficacy will be assessed for the qRT-PCR- or culture-confirmed influenza caused by any influenza A or B virus in association with a protocol-defined ILI. The vaccine efficacy (VE) is defined as

$VE = 1 - [p_V/p_P]$ , where  $p_V$  and  $p_P$  are the proportions of subjects with qRT-PCR or culture-confirmed influenza caused by any influenza A or B virus in association with a protocol-defined ILI in the M-001 experimental group and placebo group, respectively.

For the main analysis performed on the PP set,  $p_V = C_V / N_V$  with  $N_V$  = number of subjects in the PP set in vaccine M-001 group and  $C_V$  = number of cases of qRT-PCR- or culture-confirmed

influenza in association with a protocol-defined ILI in the set of  $N_V$  subjects, and similarly for the placebo group with  $p_P = C_P / N_P$ .

The two-sided confidence interval for VE will be calculated by an exact method conditional on the total number of cases in both groups. VE can also be written as

$$VE = 1 - \left[ \frac{N_P}{N_V} x \frac{q}{1-q} \right], \text{ where } q = \frac{C_V}{C_V + C_P}.$$

Given the total number of cases, an exact confidence interval for  $q$  can be derived by the exact Clopper-Pearson method for the binomial proportion from which an exact 95% CI for VE can be derived.

The exact 95% CI for  $p_V$  and  $p_P$  within each group will be derived using the Clopper-Pearson exact method.

The conditional binomial test is testing about the probability an event falls in the vaccine rather than placebo group ( $q = \frac{C_V}{C_V + C_P}$ ).

The p-value resulting from the test of  $H_0: q \leq 0.6 * N_V / (0.6 * N_V + N_P)$  versus  $H_a: q > 0.6 * N_V / (0.6 * N_V + N_P)$  will be reported (test will be performed at the one-sided level 0.025).

The p-value of the exact test will be reported together with the exact 95% CI for the VE.

The main analysis performed on the PP set will be supported by an analysis on the ITT set. For the ITT set,  $N_V$  and  $N_P$  correspond to the number of subjects in the ITT set in the M-001 and placebo groups, respectively.

VE and 95% CI will be provided by cohort, age group, and combination of cohort and age group as well for the PP and ITT population.

Descriptive statistics of  $p_V = C_V / N_V$  and  $p_P = C_P / N_P$  by country and site within country will be provided,  $N_V$  et  $N_P$  being the number of subjects and  $C_V$  and  $C_P$  being the number of cases, within each country, and site within country.

Sensitivity analyses for the primary efficacy endpoint:

Time to first qRT-PCR- or culture-confirmed influenza in association with a protocol-defined ILI will be considered.

For this analysis, performed on the PP set, the following proportional hazard model will be fitted:

$$h(t) = h_0(t) \exp[\beta_1 \text{ Group}]$$

where  $h_0(t)$  is the baseline hazard function, Group is the treatment variable, (0 for placebo and 1 for M-001), and  $\beta_1$  is the group effect.

The proportional hazard model assumes that the ratio of the hazard functions associated with M-001 and placebo is constant over time.

Under this model, the VE between M-001 and placebo is estimated by  $100(1 - e^{\beta_1})$  and its associated 95% CI will be derived as  $100(1 - e^{\beta_1 \pm z_{0.975} \text{sterr}(\beta_1)})$ , where  $\text{sterr}$  and  $z_{0.975}$  represents the standard error and 97.5% quantile for the normal distribution, respectively.

The p-value resulting from the test of  $H_0: \beta \geq \ln(0.6)$  versus  $H_a: \beta < \ln(0.6)$  will be reported (test will be performed at the one-sided level 0.025).

In addition, the time to first qRT-PCR- or culture-confirmed influenza in association with a protocol-defined ILI will be presented using a Kaplan-Meier plot, with x-axis values at 30, 60, 90, 120, 150, 180, 210 and 240 days.

For the time-to-event analysis, the time of the first qRT-PCR or culture confirmed influenza in association with a protocol-defined ILI is the time of the first symptom associated with the ILI episode. This time will be calculated in days from the start of the surveillance period (14 days post second vaccination). Subjects without qRT-PCR- or culture-confirmed influenza will be censored at the last successful contact and the associated time in the analysis will be the number of days from the start of the surveillance period (14 days post second vaccination) until censoring time. For the ITT analysis, subjects with no surveillance contact will be censored at day 1.

Additional analyses will be performed to assess the effect of the 2 cohorts (season 2018-2019 and season 2019-2020) and the age stratification factor (<65 years and  $\geq 65$  years) in the model applied to time to first qRT-PCR- or culture-confirmed influenza in association with a protocol-defined ILI. The methodology will be based on the paper by Mehrotra, Lu, and Lixix. The hazard ratio will first be estimated separately for each of the 4 strata (combinations of cohort and age group) using an unstratified Cox model and the stratum-specific estimates will be combined using the minimum risk weights.

*qRT-PCR Cut-off for confirmation of influenza in association with a protocol-defined ILI*

An additional sensitivity analysis to the primary efficacy assessment will be performed where qRT-PCR- confirmed influenza is defined if the qRT-PCR Ct count corresponding to the detection of any flu type is  $< 40$ .

The analysis will be the same than the one described for the primary efficacy endpoint.

Secondary efficacy endpoints:

The first secondary efficacy assessment will be analyzed using the same methodology as the one used for the primary outcome(including the supportive and sensitivity analyses). Notice that samples with cycle threshold (Ct)  $\leq 35$  only were grown for culture.

The second secondary efficacy assessment consisting in the between-group difference in number of days with respiratory or systemic symptoms will be assessed within the subjects with qRT-PCR- or culture-confirmed influenza illness from the per-protocol population. The number of days with respiratory or systemic symptoms during the first qRT-PCR- or culture-confirmed ILI event will be used in the analysis.

The between-group comparison will be done on the percentage of subjects with number of days with respiratory or systemic symptoms in the following categories:

- $< 7$  days
- $\geq 7$  and  $< 14$  days
- $\geq 14$  and  $< 21$  days
- $> 21$  days

using Cochran-Mantel-Haenszel test (general association statistic) with 4 strata corresponding to the combination of age category and cohort.

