11.1. Study Hypotheses

The null hypothesis of vaccine efficacy (VE) equals 40% against the alternative hypothesis $VE > 40\%$ will be tested using the two-sided, 95% Clopper-Pearson confidence interval for VE. If the lower bound of the 95% confidence interval is above 40%, adequate efficacy will have been established.

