### **10.1.1 Presentation of Results**

All analyses will use SAS® version 9.3 or higher. Unless otherwise specified, summary tables will be presented by vaccine group, labelled as follows: M-001 and Placebo.

All data will be presented in listings, sorted by country, site number and subject number, and group. Continuous variables will be summarised by the number of observations, mean, standard deviation, median, minimum, and maximum. Categorical variables will be summarized by frequency counts and percentages for each category. Unless otherwise stated, percentages will be calculated out of the population total for the corresponding group.

The minimum and maximum will be reported to the same number of decimal places as the raw data recorded in the database. The mean, median, and standard deviation will be reported to one more decimal place than the raw data recorded in the database. The maximum number of decimal places presented for any statistic shall be four.

Percentages will be presented to one decimal place except if percentage are smaller than 0.1%.

All confidence intervals (CIs) will be two-sided 95% CIs, unless stated otherwise, and presented to one more decimal place than the raw data recorded in the database. If a model is used to estimate the treatment difference, the corresponding CI according to the model will be presented. Otherwise, the unadjusted CI will be used. Nominal p-value will be presented for the main efficacy variable, but these cannot be interpreted in terms of statistical significance.

The presentation of p-values will be to three decimal places unless a p-value is less than 0.001, in which case “<0.001” will be displayed.

A month is operationally defined to be 30.4 days. A year defined to be 365 days.

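### SAP 5.4.2 states the exact test for the primary endpoint in the wrong direction; programmed as written, it would put a reversed p-value beside a correctly directed confidence interval

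*SAP*

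**What the plan says.** SAP 5.4.1 sets the null hypothesis as VE of 40% or less and gives the decision rule: "The hypothesis will be rejected and the superiority of M-001 demonstrated if the lower bound of the two-sided 95% CI for VE is" above 40% in the per-protocol analysis. Protocol 11.1 has the same direction: "If the lower bound of the 95% confidence interval is above 40%, adequate efficacy will have been established".

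SAP 5.4.2 (Primary efficacy endpoint) then sets up the exact conditional analysis. It defines q = C_V/(C_V + C_P), the probability that a case falls in the vaccine arm, and writes VE = 1 − (N_P/N_V) × q/(1 − q). The null is q at or below 0.6 N_V/(0.6 N_V + N_P). The alternative is "H_a: q > 0.6 * N_V / (0.6 * N_V + N_P", tested at one-sided 0.025. The result is to be shown: "The p-value of the exact test will be reported together with the exact 95% CI for the VE".

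Three later statements matter:

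- The Cox sensitivity test of the same endpoint uses the alternative "H_a: \beta < \ln(0.6".
- The method is reused. For the Ct < 40 sensitivity analysis: "The analysis will be the same than the one described for the primary efficacy endpoint". For culture-confirmed influenza: "The first secondary efficacy assessment will be analyzed using the same methodology as the one used for the primary outcome".
- SAP 10.1.1 says of nominal p-values for the main efficacy variable that "these cannot be interpreted in terms of statistical significance".

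**The concern.** A better vaccine leaves fewer cases in the vaccine arm, so evidence for VE above 40% is a small q. The alternative in SAP 5.4.2 looks for a large q. It is therefore a test that the vaccine falls short of 40%, placed where the plan means to show that it exceeds 40%.

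The p-value must be presented with the CI in the primary efficacy result of a pivotal trial. A programmer who follows the text would produce a value near 1 for a clear success and a very small value for a vaccine with no effect. Anyone reading it as the test of VE above 40% would be misled, and the analyses that reuse the method would carry the same error.

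**Working it through.** **Inputs**

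- Margin of 40%: SAP 5.4.1 and protocol 11.1.
- Design of 182 cases, true VE 62%, 80% power, 1:1 randomization: SAP 3.4 and protocol 11.3.2.
- Definition of q, the VE formula and the boundary: SAP 5.4.2.
- Assumption: equal per-protocol arms (N_V = N_P), relaxed at the end.

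**Direction**

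Solve VE = 0.4 in the SAP's formula: (N_P/N_V) × q/(1 − q) = 0.6, so q = 0.6 N_V/(0.6 N_V + N_P). The boundary is right for any pair of arm sizes. Because q/(1 − q) increases with q, VE decreases with q. Hence:

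- VE > 40% is the same as q **below** the boundary.
- The hypotheses in 5.4.2 are therefore H0: VE ≥ 40% against Ha: VE < 40%.
- The Cox line is correctly directed: β < ln 0.6 means a hazard ratio below 0.6, that is VE above 40%.

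**The plan's own figure**

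With equal arms the boundary is q0 = 0.6/1.6 = 0.375. At VE 62%, q = 0.38/1.38 = 0.2754. With n = 182, the Clopper-Pearson lower limit for VE exceeds 40% when C_V ≤ 55. Then:

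- P(X ≤ 55 | 182, 0.375) = 0.0242, the actual one-sided error rate.
- P(X ≤ 55 | 182, 0.2754) = 0.815, the power.

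The stated 80% is reproduced, and it belongs to the correctly directed test.

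**As written against corrected, 182 cases**

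As written, p = P(X ≥ C_V | 182, 0.375). Corrected, p = P(X ≤ C_V | 182, 0.375).

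| Vaccine vs placebo cases | VE | 95% CI for VE | CI rule | p as written | p corrected |
|---|---|---|---|---|---|
| 50 vs 132 | 62.1% | 47.2% to 73.2% | met | 0.998 | 0.0028 |
| 55 vs 127 | 56.7% | 40.1% to 69.0% | met | 0.983 | 0.0242 |
| 56 vs 126 | 55.6% | 38.6% to 68.2% | not met | 0.976 | 0.0347 |
| 75 vs 107 | 29.9% | 5.0% to 48.5% | not met | 0.169 | 0.866 |
| 82 vs 100 | 18.0% | −10.9% to 39.5% | not met | 0.022 | 0.985 |
| 91 vs 91 | 0% | −35.2% to 26.0% | not met | 0.0004 | 0.9998 |

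- At every split that meets the CI rule (C_V ≤ 55), the p-value as written is at least 0.983.
- As written, the test rejects at 0.025 only when C_V ≥ 82. The chance of that is about 3 in 10 million at true VE 62%, and 92% at true VE 0%.
- The corrected test agrees with the CI rule at every C_V from 1 to 181.

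**Unequal arms**

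For 50 against 132 cases:

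| N_V/N_P | Boundary | p as written | p corrected |
|---|---|---|---|
| 0.95 | 0.363 | 0.995 | 0.0073 |
| 1.05 | 0.387 | 0.999 | 0.0010 |

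**The case against.** The strongest reply is that nothing depends on this p-value. Both documents define success by the lower CI limit, and SAP 10.1.1 already calls the p-value nominal. The intended direction is plain from SAP 5.4.1, protocol 11.1 and the Cox line, so a careful programmer may well correct it. Nothing in the documents shows how the test was programmed. All of this stands. It limits the error to a reported statistic and makes the consequence conditional on the text being followed.

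It is also fair to say that the p-value as written is a valid test of the opposite hypothesis and does not clash with the CI at every split. For failing results with 56 to 81 vaccine cases it runs from 0.976 down to 0.031, which is not very small. From 82 cases upward, a value below 0.025 agrees with a CI lying wholly below 40%. The harm lies in reading it as the test of VE above 40%.

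Two points on scope also stand. The SAP supports the per-protocol analysis with an ITT analysis but does not expressly ask for an ITT p-value. The disagreement between 5.4.2 and 10.1.1 is a separate matter and adds no weight to the sign error.

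None of this makes the stated hypotheses right. Leaving the programmer to correct them means an undocumented departure from the SAP on the primary endpoint. A misreading of the PDF is unlikely, because both signs are reversed together while the signs in 5.4.1 and in the Cox test read correctly.

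**Conclusion.** The hypotheses for the exact test in SAP 5.4.2 are reversed. This follows from the SAP's own definitions and needs no assumption about the data. The boundary value is correct; only the two inequality signs are wrong.

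If programmed as written, the p-value for the primary endpoint would be the wrong binomial tail. The sizes above assume 182 cases and equal per-protocol arms, and a 5% imbalance either way changes them little. The Ct < 40 and culture-confirmed analyses inherit the error, as would any p-value given for ITT.

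The CI success rule, the type I error of the primary decision, the power and the sample size are untouched. This should be fixed, but it does not threaten the trial's conclusion.

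Separately, 5.4.2 runs the test at a stated one-sided level of 0.025, while 10.1.1 denies the p-value any reading as statistical significance. The SAP should say which applies.

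**What to change.** In SAP 5.4.2, replace the hypotheses with H0: q ≥ 0.6 N_V/(0.6 N_V + N_P) against Ha: q < 0.6 N_V/(0.6 N_V + N_P), one-sided 0.025. State that p = P(X ≤ C_V), with X binomial on C_V + C_P trials and the boundary as its probability. Apply the corrected line to the Ct < 40 and culture-confirmed analyses, and to ITT if a p-value is shown there.

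Reconcile 5.4.2 with 10.1.1 in one of two ways: exempt the primary test from the sentence in 10.1.1, or state that the p-value is supportive and the CI is the only success criterion.

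The cost is one line in 5.4.2, one sentence in 10.1.1 and one program option, ideally before unblinding. The CI rule, power and sample size stay as they are.

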11.5.3. Analysis of Efficacy Data

Primary Efficacy Assessment

For the primary analysis of vaccine efficacy (VE), the efficacy of M-001 after a first influenza season in each cohort will be estimated by

$$VE = 1 - [(C_V / N_V) / (C_P / N_P)]$$

where C_V and C_P are the number of per protocol cases of influenza meeting the primary case definition in the vaccine and placebo group, respectively, and N_V and N_P are the number of per protocol subjects in the vaccine and placebo group, respectively. The confidence interval for VE will be calculated by the Clopper-Pearson exact method conditional on the total number of cases in the vaccine and placebo groups combined. Similarly, vaccine efficacy and its 95% confidence interval will be calculated for the ITT population.

VE and its 95% confidence interval will be estimated by age group (i.e., < 65 years, ≥ 65 years) for both the PP and ITT analysis populations. Given VE for a specific age group can be approximated

by 1 minus the age group specific odds ratio, the Breslow-Day test for the homogeneity of the odds ratios will be used to test for a common VE across age groups. In addition, given that circulating strains of flu may vary over the course of the trial, VE and its 95% confidence interval will be estimated by flu season as well for both the PP and ITT analysis populations; Breslow-Day test for the homogeneity of the odds ratios will be used to test for a common VE across cohort (flu season).

If the study discontinuation or loss to follow-up rate varies by vaccine group, a Cox proportional hazards model will be used to estimate vaccine efficacy. For this analysis, time from 15 days after the second dose of study vaccine or placebo to the first episode of culture or PCR confirmed influenza caused by any influenza A or B virus in association with a protocol-defined influenza like illness (ILI) will be the endpoint. All subjects will be censored at the earliest of their date of study withdrawal, date of lost to follow-up, or end of their first influenza season defined as April 30th for countries in the northern hemisphere. The model will have a single covariate for vaccine group and will be stratified by age group. Vaccine efficacy will be estimated by 1 minus the estimated hazard ratio from this model. If the lower limit of the 95% confidence interval for vaccine efficacy based on the PP population is above 40%, the vaccine will have demonstrated sufficient efficacy.

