## 5. EFFICACY ENDPOINTS

### 5.1 Efficacy Endpoints – Definition

#### Surveillance for respiratory illness – Flu season 2018-2019

- *Active Surveillance:* All subjects were contacted twice a week by a call center starting on November 15th of the vaccination year until the week of March 31th the following year.
- *Passive Surveillance:* All subjects were instructed to contact their study site if they experienced symptoms of a respiratory illness from Day 14 post-second vaccination day until May 15th the following year.

Note: Active surveillance might be extended by the medical monitor for those countries in which influenza does not reach low levels by March 30.

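### Censoring event-free subjects at their last contact departs from the protocol without being declared, and can bias the tail of the season 1 Kaplan-Meier curve upward

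*SAP*

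**What the plan says.** The rule under review is in SAP 5.4.2, in the time-to-event sensitivity analysis: "Subjects without qRT-PCR- or culture-confirmed influenza will be censored at the last successful contact". Time zero is defined just before it: "This time will be calculated in days from the start of the surveillance period (14 days post second vaccination"). The same analysis includes a "Kaplan-Meier plot, with x-axis values at 30, 60, 90, 120, 150, 180, 210 and 240 days". One further sentence deals with people who were never reached: "For the ITT analysis, subjects with no surveillance contact will be censored at day 1".

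Protocol 11.5.3 has a different rule for its Cox model. Each participant "will be censored at the earliest of their date of study withdrawal, date of lost to follow-up, or end of their first influenza season", and that season end is fixed as 30 April for northern-hemisphere countries. SAP section 11, which lists departures from the protocol, does not mention censoring.

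The surveillance calendar matters here:

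- **Cohort 1 calls:** twice weekly to 31 March 2019 (Protocol Table 3; SAP 5.1). A note in SAP 5.1 lets the medical monitor extend them in countries where influenza is not yet low.
- **Cohort 1 swabs:** 15 September 2018 to 30 April 2019, extendable (Protocol Table 3 and 7.3).
- **Passive reporting:** subjects were "instructed to contact their study site if they experienced symptoms of a respiratory illness from Day 14 post-second vaccination day", until 15 May.
- **Visit 4:** one call or message to everyone, 180 ± 14 days after dose 2 (Protocol 7.4).
- **Cohort 2 calls:** to 31 March 2020 in Protocol Table 4 and 7.5, but to 30 April 2020 in SAP Table 2 and 5.1.

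SAP 5.4.2 does not define a successful contact. SAP 8.3 counts an answered call, any phone contact or a visit as last contact.

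**The concern.** In cohort 1, routine calls can stop a month before swabbing does. In that month a healthy subject has no scheduled reason to make contact unless Visit 4 happens to fall there, so the SAP rule removes that subject at the last call or Visit 4. A subject who becomes ill in April does make contact and is either counted as a case or kept at risk longer. Whether someone stays in the late risk set then depends on being ill. That is informative censoring, and it pushes the Kaplan-Meier incidence up.

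The curves are the only efficacy figures in the SAP's output list (Figures 14.2.1.1 to 14.2.1.3), and their axis extends into the exposed region. A season 1 curve ending well above the case proportion in its companion table would confuse readers. SAP 5.4.2 also carries the primary endpoint's sensitivity analyses over to the culture-confirmed secondary endpoint, so the rule would apply there too.

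**Working it through.** **1. The plan's own figure.** The documents state no Kaplan-Meier incidence, only the sizing: 182 cases, 12,000 subjects, 80% power, VE 62% against 40%. With the exact conditional binomial, q0 = 0.6/1.6 = 0.375 and q1 = 0.38/1.38 = 0.2754. At 182 cases, success needs at most 55 vaccine cases, which gives power 0.815 and one-sided alpha 0.0242. The sample size is 2 × 182 / (1.38 × 0.0241) / 0.9 = 12,161, against 12,000 stated. The sizing is reproduced if 2.41% is the placebo rate, and that rate is used below.

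**2. Where the exposed stretch lies.** If time zero is 15 September 2018 (dose 2 on 1 September), 31 March is day 197, 30 April day 227 and 15 May day 242. Visit 4 falls at 180 ± 14 − 14, that is days 152 to 180. Dose 2 on 1 September puts nominal Visit 4 on 28 February, leaving all of April uncovered. Dose 2 on 1 November puts it on 30 April, leaving no gap. Dose-2 dates therefore matter.

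**3. Size of the late risk set.** Cohort 1 has about 4,055 × 0.9 / 2 = 1,825 per-protocol placebo subjects. The simulation used these assumptions, which are not in the documents: dose 2 in three windows between 1 September and mid-November, 3% with a late illness contact, and 5% lost. With Visit 4 counted:

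| Day | At risk, SAP rule | At risk, 30 April rule |
|---|---|---|
| 150 | 90-92% | 93% |
| 180 | 4-22% | 36-67% |
| 200 (the two September-start windows) | about 1% | 27-34% |

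**4. What one late case does.** If incidence is already 2.41% and one case occurs with r at risk, the curve moves to 1 − (1 − 0.0241)(1 − 1/r). About 1% of 1,825 is 18 people, and 27% is 493. For r = 20 the result is 7.3%; for r = 500 it is 2.6%. Few such cases are needed: 1,825 × 0.0241 = 44 placebo cases, so a 5% April share is about 2 cases and 10% about 4.

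**5. Effect on the curve.** The table gives the ratio of Kaplan-Meier incidence at the last event, SAP rule over 30 April rule. Figures are medians of 25 runs, with ranges over scenarios and 3,600 placebo subjects in cohort 2.

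| Cases in April | Cohort 1 | Pooled, cohort 2 calls to 31 March (protocol) |
|---|---|---|
| 0% | 1.0-1.1 | 1.0-1.1 |
| 2% | 1.0-1.3 | 1.0-1.5 |
| 5% | 1.0-2.6 | 1.7-2.4 |
| 10% | 1.2-3.7 | 2.1-3.5 |

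With cohort 2 calls to 30 April, as in the SAP, the pooled ratio is 1.00-1.12 over all shares, and cohort 2 alone gives 1.00-1.03. Under the 30 April rule the curve stays at about 2.3-2.8% throughout. At day 180 the two rules differ by at most about 17%.

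A second cohort 1 simulation had everyone reached at the last calls and Visit 4, 3% with an influenza-negative April contact, and 200 runs per window. By day 240 it gave 2.7-3.1% against 2.4-2.5% at a 2% April share, 3.5-6.0% against 2.5-2.6% at 5%, and 9.5-10.0% against 2.6-2.7% at 10%.

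If only call-centre contacts count as successful, the last step in cohort 1 can reach 100%, when the last person at risk is a case. This was run for one dose-2 window.

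**6. Effect on VE.** Cox VE agreed to three decimals under the two rules in all eight settings (for example 0.627 and 0.627), with both arms contacted alike. The primary VE is a ratio of proportions and uses no censoring times.

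**The case against.** The case against giving this weight is substantial. The SAP's own cohort 2 dates run calls to the end of the swab period, which removes the gap for the larger cohort. In cohort 1 the calls may be extended in just those countries where influenza persists, and the simulations do not model that. Visit 4 reaches everyone. Most of the curve is sound, because the risk sets nearly agree at day 150. With time zero at 15 September or later, routine swabbing ends by day 227, so the plotted value at day 240 is only carried forward. The figures and Cox tables are not marked as top-line, and the analysis is a sensitivity analysis.

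All of this limits the scope and size, and it stands. It does not remove the problem. The call extension is discretionary, and Visit 4 falls before 31 March for early-dosed subjects. SAP section 11 adds that the SAP gives more detail than the protocol, but a different censoring rule is a replacement and not a detail.

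A reader might infer that all three figures will overstate incidence several-fold, or that the efficacy estimate is biased. The documents support neither. The first needs an April case share they do not give and, for the pooled and season 2 figures, the protocol's call dates in place of the SAP's. The second fails because the primary analysis uses proportions and the hazard ratio barely moves.

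**Conclusion.** The point holds in limited form and should be corrected. The SAP replaces the protocol's censoring rule without declaring it, and the new rule ties late follow-up to illness-triggered contact. The practical harm is a possibly distorted tail, beyond about day 180 to 200, of the season 1 curve (Figure 14.2.1.2).

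The upward bias there is about 1.0- to 1.3-fold if 0-2% of cases start in April, and can reach several-fold at about 5-10% or more. This rests on assumed dose-2 dates, late-contact rates and April shares, and on calls not being extended. Figures 14.2.1.1 and 14.2.1.3 are materially affected only if cohort 2 calls end on 31 March; under the SAP's date the effect is about 1.0- to 1.1-fold. No efficacy conclusion changes: primary VE is untouched and Cox VE is essentially the same.

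**What to change.** In SAP 5.4.2, replace the censoring sentence with: Subjects without confirmed influenza are censored at the earliest of withdrawal, death, documented loss to follow-up, or the end of the swab-collection window for their country (30 April unless extended). Apply it to the Cox models and all Kaplan-Meier figures.

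Reconcile the cohort 2 end of active surveillance between the protocol (31 March) and the SAP (30 April). Print numbers at risk under each curve. If last-contact censoring is kept instead, declare it in section 11 and define a successful contact.

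The cost is one sentence and one derived date. The downside is that subjects silent after their last call are assumed to be still under passive surveillance. The primary count analysis already makes that assumption.
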